9.3 Additional Efficacy Analyses

Secondary Analysis of the Primary Efficacy Variables

Analysis of covariance (ANCOVA) analyses will be carried out on change from baseline to final NMSS total score and change from baseline to final PDSS-2 total score. The ANCOVA model will contain treatment and country as the main effects and baseline score as the covariate. Sensitivity analyses will be carried out on the above variables with the same ANCOVA model using all randomized subjects. In this analysis, Baseline

Observation Carried Forward (BLOCF) will be applied to subjects who do not have post-randomization assessment of NMSS or PDSS-2.

Analysis of Secondary Efficacy Variables

The MMRM model, and the descriptive statistic summary described for the NMSS and PDSS-2 total score will also be used to evaluate the change from baseline in each of the following efficacy endpoints:

- UPDRS Part II score
- Parkinson's Disease Questionnaire-8 (PDQ-8) summary index
- NMSS domain scores
- PDSS-2 domain scores
- UPDRS total score, Part I score, Part III score, Part IV score
- Parkinson Anxiety Scale (PAS) total and subscale scores
- Geriatric Depression Scale (GDS-15)
- King's PD Pain Scale total and domain scores

For CGI-C and PGIC, an analysis of variance (ANOVA) model containing treatment and country as the main effects will be carried out.

UPDRS Part II score, CGI-C score and PDQ-8 summary index are key secondary endpoints. If both primary efficacy variables are statistically significant after adjusting for multiplicity, the Stepwise Gatekeeping Procedure will be utilized and the 3 key secondary endpoints will be tested using the Hochberg procedure with significance level of 0.05. Specifically, the following steps will be followed:

- If the largest of the 3 P values is ≤ 0.05 (i.e., all 3 P values are ≤ 0.05), all 3 key secondary endpoints are considered statistically significant.
- If the largest of the 3 P value is > 0.05 , then compare the middle P value with 0.025. The second and third key secondary endpoints are both statistically significant if the middle P value is ≤ 0.025 .

- If the largest of the 3 P value is > 0.05 and the middle P value is > 0.025 , then compare the smallest P value with 0.0167. If the smallest P value is ≤ 0.0167 , then the third key secondary endpoint is statistically significant. Otherwise, none of the 3 key secondary endpoints can be considered statistically significant.

All secondary efficacy variables will be summarized by the number of subjects with non-missing data, mean, standard deviation, median, minimum and maximum. CGI-C and PGIC variables will also be summarized by the number of subjects with non-missing data and the number and percentage of subjects in each response category. In addition, the summary of the PGIC will also include the number and percentage of subjects reporting improvement (response of either "very much improved," "much improved," or "minimally improved").

9.4 Calculation of Efficacy and Health Outcome Variable

The primary and secondary efficacy variables derived from the above measures are presented in [Table 7](#).

Table 7. Primary and Secondary Efficacy Variables, and Derivations

Instrument	Efficacy Variable	Derivation	Range/Direction	
NMSS: 30 questions, 9 domains (cardiovascular/falls, sleep/fatigue, mood/cognition, perceptual problems/hallucinations, attention/memory, GI tract, urinary, sexual function, miscellaneous). Score of each question is calculated by multiplying severity*frequency. Severity and frequency are rated using a scale ranging from 0 (none) to 3 (severe) for severity and from 1 (rarely) to 4 (very frequent) for frequency. There is no imputation of missing responses. If one or more item scores are missing, the total score and respective domain score will not be calculated.	Cardiovascular/falls	Sum of Questions 1 – 2	0 – 24/lower value desirable	
	Sleep/fatigue	Sum of Questions 3 – 6	0 – 48/lower value desirable	
	Mood/cognition	Sum of Questions 7 – 12	0 – 72/lower value desirable	
	Perceptual problems/hallucinations	Sum of Questions 13 – 15	0 – 36/lower value desirable	
	Attention/memory	Sum of Questions 16 – 18	0 – 36/lower value desirable	
	GI tract	Sum of Questions 19 – 21	0 – 36/lower value desirable	
	Urinary	Sum of Questions 22 – 24	0 – 36/lower value desirable	
	Sexual function	Sum of Questions 25 – 26	0 – 24/lower value desirable	
	Miscellaneous	Sum of Questions 27 – 30	0 – 48/lower value desirable	
	Total score	Addition of 9 domains	0 – 360/lower value desirable	
	PDSS-2: 15 questions, 3 domains. Score of each question is based on a 5-point Likert-type scale (ranging from 0 [never] to 4 [very often]). There is no imputation of missing responses. If one or more item scores are missing, the total score and respective domain score will not be calculated.	motor symptoms at night	Sum of Questions 1 – 5	0 – 20/lower value desirable
		PD symptoms at night	Sum of Questions 6 – 10	0 – 20/lower value desirable
		disturbed sleep	Sum of Questions 11 – 15	0 – 20/lower value desirable
Total score		Addition of 3 domains	0 – 60/lower value desirable	

Table 7. Primary and Secondary Efficacy Variables, and Derivations (Continued)

Instrument	Efficacy Variable	Derivation	Range/Direction
UPDRS: 42 questions, Part I (Questions 1 – 4), Part II (Questions 5 – 17), Part III (Questions 18 – 31), and Part IV (Questions 32 – 42). Questions 35 – 38 and 40 – 42 are 2-point (0 and 1), all other questions are 5-point (0 – 4).	Part I score	Sum of Questions 1 – 4. No missing answers will be imputed so Part I score will be missing if any of the answers are missing.	0 – 16/lower value desirable
	Part II score	Sum of Questions 5 – 17. Part II score will be calculated as long as at least 12 questions have been answered. If 1 answer is missing the Part II score will be calculated by multiplying the sum of questions answered by the ratio of the total number of Part II questions to the number of questions answered.	0 – 52/lower value desirable
	Part III score	Sum of Questions 18 – 31 with Questions 20 – 26 apply to multiple body parts, resulting in 27 answers total. Part III score will be calculated as long as at least 23 answers have been recorded. If 4 or fewer answers are missing the Part III score will be calculated by multiplying the sum of the answers provided by the ratio of the total number of Part III answers possible (27) to the number of answers provided.	0 – 108/lower value desirable
	Total score (Part I, II, III)	Sum of Part I, Part II, Part III scores. Will be missing if any one of Part I, Part II, Part III scores is missing.	0 – 176/lower value desirable

Table 7. Primary and Secondary Efficacy Variables, and Derivations (Continued)

Instrument	Efficacy Variable	Derivation	Range/Direction
UPDRS: 42 questions, Part I (Questions 1 – 4), Part II (Questions 5 – 17), Part III (Questions 18 – 31), and Part IV (Questions 32 – 42). Questions 35 – 38 and 40 – 42 are 2-point (0 and 1), all other questions are 5-point (0 – 4). (continued)	Part IV score	Sum of Questions 32 – 42. Part IV score will be calculated as long as at least 10 answers have been recorded. If 1 answer is missing the Part II score will be calculated by multiplying the sum of the answers provided by the ratio of the total number of Part III answers possible to the number of answers provided.	0 – 23/lower value desirable
CGI-C: 7-point scale (1 = very much improved, 2 = much improved, 3 = minimally improved, 4 = no change, 5 = minimally worse, 6 = much worse, 7 = very much worse)	CGI-C score	7-point score as collected	1 – 7/lower score desirable
PDQ-8: 8 question including the mobility, activities of daily living, emotional well-being, stigma, social support, cognition, communication, bodily discomfort. 5-point scale: 0 = Never, 1 = Occasionally, 2 = Sometimes, 3 = Often, 4 = Always (or cannot do at all, if applicable).	PDQ-8 Summary Index (PDQ-SI)	Sum of each question divided by 32 and multiplied by 100. The PDQ-8 total score will be calculated as long as at least 7 questions have been answered. Missing values in a question will be replaced by the patient population's mean of the question, and rounded to an integer.	0 – 100/lower value desirable
PGIC: patient's opinion of degree of change since beginning care at the clinic, 7-point scale (1 = no change, 2 = almost the same, 3 = a little better, 4 = somewhat better, 5 = moderately better, 6 = better, 7 = a great deal better)	PGIC score	7-point score as collected	1 – 7/higher score desirable

Table 7. Primary and Secondary Efficacy Variables, and Derivations (Continued)

Instrument	Efficacy Variable	Derivation	Range/Direction

King's PD Pain Scale: 14 items addressing the following 7 domains (musculoskeletal pain, Chronic pain, fluctuation-related pain, nocturnal pain, orofacial pain, neuropathic pain, radicular pain). Each item is scored by severity (0, none to 3, very severe) multiplied by frequency (0, never to 4, all the time) resulting in a subscore of 0 to 12, the sum of which gives the total score with a range from 0 to 168.
	
King's PD Pain score
	
Sum of 14 item scores. The King's PD Pain Scale score will be calculated as long as at least 13 questions have been answered. Missing values in a question will be replaced by the patient population's mean of the question, and rounded to an integer.
	
0 – 168/lower value desirable


PAS: 12-item including 1) Feeling anxious or nervous 2) Feeling tense or stressed 3) Being unable to relax 4) Excessive worrying about everyday matters 5) Fear of something bad, or even the worst, happening 6) Panic or intense fear 7) Shortness of breath 8) Heart palpitations or heart beating fast 9) Fear of losing control 10) Social situations 11) Public settings 12) Specific objects or situations Rated as: 0, Never; 1 Rarely; 2, Sometimes; 3, Often; 4, Nearly always
	
PAS score
	
Sum of 12 item scores. The PAS score will be calculated as long as at least 11 questions have been answered. Missing values in a question will be replaced by the patient population's mean of the question, and rounded to an integer.
	
0 – 48/lower value desirable

Table 7. Primary and Secondary Efficacy Variables, and Derivations (Continued)

Instrument	Efficacy Variable	Derivation	Range/Direction

GDS-15: 15 yes/no as following 1) satisfied with life 2) Dropped many activities and interests 3) life is empty 4) Often get bored 5) In good spirits most of the time 6) Afraid that something bad is going to happen 7) Feel happy most of the time 8) Often feel helpless 9) Prefer to stay at home, rather than going out and doing things 10) Feel that have more problems with memory than most 11) Think it is wonderful to be alive now 12) Feel worthless 13) Feel full of energy 14) Situation is hopeless 15) Most subjects are better off.
 
Answer YES to question 2.3.4.6.8.9.10.12.14.15 will be scored 1 point.
 
Answer NO to questions 1.5.7.11.13 will be scored 1 point.
	GDS-15 score	Sum of 15 item scores. The GDS-15 score will be calculated as long as at least 13 questions have been answered. Missing values in a question will be replaced by the patient population's mean of the question, and rounded to an integer.	0 – 15/lower value desirable

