1 = Very much improved, 2 = Much improved, 3 = Minimally improved, 4 = No change, 5 = Minimally worse, 6 = Much worse, 7 = Very much worse.

The responses of "Very much improved," "Much improved" and "Minimally improved" on the PGIC will be used to define responders. A qualified rater will administer the PGIC to the subject at the times indicated in [Table 3](#).

Parkinson's Disease Questionnaire (PDQ-8)

The PDQ-8⁵⁴ is a disease-specific instrument designed to measure aspects of health that are relevant to subjects with PD, and which may not be included in general health status questionnaires. The PDQ-8 is a self-administered questionnaire. Each item is scored on the following 5-point scale: 0 = Never, 1 = Occasionally, 2 = Sometimes, 3 = Often, 4 = Always (or cannot do at all, if applicable).

Higher scores are consistently associated with the more severe symptoms of the disease such as tremors and stiffness. The results are presented as eight discrete domain scores and as a summary index. The PDQ-8 domain scores and summary index range from 0 to 100, where lower scores indicate a better perceived health status.

A qualified rater will administer the PDQ-8 to the subject at the times indicated in [Table 3](#).

Parkinson Anxiety Scale (PAS)

The Parkinson Anxiety Scale (PAS) is a new scale developed specifically to measure severity in anxiety in Parkinson's disease. Lack of adequate validation data in the existing anxiety scales led to the development of the PAS. The PAS is a brief scale designed to measure anxiety in PD, rated by patients or clinicians. It contains three dimensions: persistent anxiety, episodic anxiety, and avoidance behavior. It is an easy and brief to

administer, and has better clinimetric properties than existing anxiety rating scales.⁵⁵ Additionally a recent study has found that the PAS modified dimensions A and B provide valid and reliable measures of anxiety in PD that are comparable across raters.⁵⁶ A qualified rater will administer the PAS to the subject at Visits 3, 6, 7 and 8.

Geriatric Depression Scale (GDS-15)

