12.0 Summary of Changes

This SAP contains no change in analysis from the latest version of the protocol (Protocol Amendment 4).

The changes in this SAP from SAP V1.0 is: Per protocol amendments, subjects from South Korean/United States who complete the 26-week clinical study will have the option to enter an extension of the study. This SAP added the description for Extension Period analyses.

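### SAP Table 7 reverses the PGIC scale relative to the protocol, and its missing-answer rule for UPDRS Part IV uses another part's answer count (factor 2.7 instead of 1.1)

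*SAP*

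**What the plan says.** **PGIC.** Protocol 5.3.1.1 gives the anchors as "1 = Very much improved, 2 = Much improved, 3 = Minimally improved, 4 = No change", with 5 to 7 running from minimally to very much worse. It defines responders as subjects giving one of the three improved responses.

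The PGIC row of SAP Table 7 instead gives a "7-point scale (1 = no change, 2 = almost the same, 3 = a little better, 4 = somewhat better", continuing through moderately better and better to a great deal better at 7. It measures change since the start of care at the clinic, takes the score as collected, and states the range and direction as "1 – 7/higher score desirable". SAP 9.3 analyses the PGIC score by ANOVA with treatment and country, and adds that the "summary of the PGIC will also include the number and percentage of subjects reporting improvement". It then defines improvement by the protocol's three improved labels.

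**UPDRS Part IV.** Table 7 defines Part IV as the sum of Questions 32 to 42, range 0 to 23, and requires at least 10 answers. For one missing answer it says: "If 1 answer is missing the Part II score will be calculated by multiplying the sum of the answers provided", the multiplier being "the ratio of the total number of Part III answers possible to the number of answers provided". The Part III row explains that several of its questions cover more than one body part, "resulting in 27 answers total".

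SAP 12.0 declares the analyses unchanged from Protocol Amendment 4.

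**The concern.** Table 7 is where the SAP specifies how each efficacy score is built and which direction is good. SAP 3.0 says the plan's conventions are there to guide the programming. An error in this table is therefore an error in the operative rule.

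For the PGIC, the anchors, the reference point and the direction all differ from the protocol, and the Table 7 scale has no category for worsening. A lower LCIG mean is a benefit on the protocol scale but would be read as harm under Table 7. If the response-category table were labelled from Table 7, code 1 would print as no change and code 7 as the best outcome.

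For Part IV, the sentence names two wrong parts. UPDRS Parts III and IV are the named measures of the motor symptoms and complications objective (Protocol 4.0, SAP 4.5.2). Part IV is analysed as change from baseline. An inflated follow-up record would look like worsening at that visit. An inflated baseline record would add a spurious improvement to every later change score for that subject and would also distort the baseline covariate.

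**Working it through.** **1. PGIC codes side by side**

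| Code | Protocol 5.3.1.1 | SAP Table 7 |
|---|---|---|
| 1 | very much improved | no change |
| 2 | much improved | almost the same |
| 3 | minimally improved | a little better |
| 4 | no change | somewhat better |
| 5 | minimally worse | moderately better |
| 6 | much worse | better |
| 7 | very much worse | a great deal better |

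The best code is 1 in the protocol and 7 in Table 7. The improvement labels used in SAP 9.3 fit codes 1 to 3 of the protocol column and appear nowhere in the Table 7 PGIC row. The CGI-C row of the same table does carry these labels, with lower scores desirable.

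Illustration with assumed means: LCIG 3.0 and OMT 4.0 give 3.0 − 4.0 = −1.0. This favours LCIG on the protocol scale and OMT under the Table 7 direction. The estimate and its two-sided P value are the same either way.

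**2. Part IV: reproducing the stated range**

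- Questions 32 to 42 are 11 items.
- Seven are scored 0–1 (35 to 38 and 40 to 42). The other four (32, 33, 34, 39) are scored 0–4.
- Maximum = 7 × 1 + 4 × 4 = 23, as Table 7 states.

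The other UPDRS ranges also reproduce: Part II 13 × 4 = 52, Part III 27 × 4 = 108, total 16 + 52 + 108 = 176.

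**3. Part IV: the multiplier with one answer missing**

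Factor = answers possible / answers provided.

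- With the Part III count: 27 / 10 = 2.7.
- With Part IV's own count: 11 / 10 = 1.1.
- Ratio: 2.7 / 1.1 = 2.45.

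The SAP does not print 1.1. It follows from the 11 items, the 10-answer minimum and the pattern of the Part II and Part III rows, each of which uses its own count.

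**4. Size for one record**

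- Observed sum 8: 8 × 2.7 = 21.6 against 8 × 1.1 = 8.8, an excess of 12.8 points on a 23-point scale.
- Observed sum 9: 9 × 2.7 = 24.3, already above 23.
- One such subject (sum 8) in a 44-subject arm shifts the arm mean by 12.8 / 44 = 0.29 points.

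**5. Size over an arm**

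The documents give no rate of missing items. Suppose a fraction f of records has exactly one missing answer and these records have scores similar to the rest. The mean score then rises by f × (2.7 / 1.1 − 1) = f × 1.4545:

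| f (assumed) | Rise in mean score |
|---|---|
| 1% | 1.5% |
| 5% | 7.3% |
| 10% | 14.5% |

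**6. Does the factor 1.1 stay within range?**

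- If a 0–4 item is missing, the largest observed sum is 23 − 4 = 19, and 19 × 1.1 = 20.9.
- If a 0–1 item is missing, the largest is 23 − 1 = 22, and 22 × 1.1 = 24.2. A sum of 21 gives 23.1 and a sum of 20 gives 22.0.

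Only observed sums of 21 and 22 exceed 23.

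**The case against.** The strongest case on the other side is that these are clerical slips with an obvious reading.

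- The Part IV row never prints 27; that number comes from the Part III row. A sentence naming two wrong parts is better called undefined than a rule with factor 2.7. This is fair as to the literal text. But an undefined rule also needs correcting, and 27 is the only count the SAP gives for Part III.
- SAP 6.7 requires a Derived Dataset Specification, and a range check against 0–23 would catch many errors. Both make a literal 2.7 less likely. Neither corrects the SAP, and observed sums of 8 or less stay within range (8 × 2.7 = 21.6), so a range check would miss them.
- The PGIC category counts and percentage improved in SAP 9.3 would sit beside the mean and expose a reversed reading. That protection holds only if the outputs are labelled from the protocol and not from Table 7.
- The SAP 12.0 statement is weak evidence that the PGIC difference was unintended, because the SAP also moves the PGIC from MMRM (Protocol 8.1.3.2) to ANOVA without declaring it. This stands. The conflict between SAP 9.3 and Table 7 is the better evidence.
- The percentages in the working concern mean scores, not the treatment difference, and rest on assumed missingness. This also stands. The distortion of the difference depends on how affected records fall between arms and visits, which cannot be known from the documents.

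**Conclusion.** Both errors are confirmed. Table 7 contradicts the protocol and SAP 9.3 on the PGIC anchors and direction. Its Part IV rule either defines no Part IV score when one answer is missing or, applied to Part IV, inflates that record 2.45-fold.

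The reach is limited. PGIC data, estimate and P value do not change; only the stated direction and possibly the printed labels do. Complete Part IV records are plain sums, and records with two or more missing answers are not scored, so neither is affected. Part IV is outside the UPDRS total, which covers Parts I to III. Neither endpoint is in the primary or key secondary Hochberg family, and the sample size is not involved.

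The factor comparison is exact arithmetic. The arm-level figures rest on assumed missing-item rates, and the PGIC illustration on assumed means. Which PGIC form was actually collected cannot be seen from the documents. The point should be fixed, but it does not threaten the trial's main conclusions.

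**What to change.** 1. Check the PGIC page of the eCRF. If it is the protocol form, replace the PGIC row of Table 7 with the protocol anchors, mark lower scores as desirable, and state improvement as codes 1 to 3 so that it matches SAP 9.3. If another form was collected, the protocol scale and the SAP 9.3 improvement definition must be reconciled with it instead.
2. In the Part IV row, name the Part IV score and set it, for one missing answer, to the sum of the answers × 11 / number answered, capped at 23. The cap is a small addition that keeps scores within the stated range; it acts only on observed sums of 21 and 22.

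The cost is two table rows in the SAP and one check of an eCRF page, with no effect on data collection or sample size.

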9.5 Handling of Multiplicity

The two-sided P values obtained from the MMRM model for NMSS total score change from baseline to Week 26 and PDSS-2 total score change from baseline to Week 26 will be adjusted for multiplicity using the Hochberg procedure. This method controls the family-wise error rate (FWER) at a pre-specified significance level ($\alpha = 0.05$). Specifically, the following steps will be followed:

- If the larger of the 2 P values is ≤ 0.05 (i.e., both P values are ≤ 0.05), both endpoints are considered statistically significant.
- If the larger of the 2 P value is > 0.05 , then compare the smaller P value with 0.025. The second endpoint is statistically significant if the P value is ≤ 0.025 ; otherwise, neither endpoint is considered statistically significant.

If both primary efficacy variables are statistically significant after adjusting for multiplicity, the Stepwise Gatekeeping Procedure will be utilized and the 3 key secondary endpoints (UPDRS Part II score, CGI-C score and PDQ-8 summary index) will be tested using the Hochberg procedure with significance level of 0.05. Specifically, the following steps will be followed:

- If the largest of the 3 P values is ≤ 0.05 (i.e., all 3 P values are ≤ 0.05), all 3 key secondary endpoints are considered statistically significant.
- If the largest of the 3 P value is > 0.05 , then compare the middle P value with 0.025. The second and third key secondary endpoints are both statistically significant if the middle P value is ≤ 0.025 .
- If the largest of the 3 P value is > 0.05 and the middle P value is > 0.025 , then compare the smallest P value with 0.0167. If the smallest P value is ≤ 0.0167 , then the third key secondary endpoint is statistically significant. Otherwise, none of the 3 key secondary endpoints can be considered statistically significant.

